5.6.1. Measurable Disease Definitions

Important inclusion criteria for this trial include the presence of measurable disease with at least one target lesion to use for all disease assessments.

Measurable lesions are defined as those that can be accurately measured in at least one dimension (longest diameter to be recorded) as ≥ 20 mm by chest x-ray or as ≥ 10 mm with CT or MRI scan, or calipers by clinical exam. All tumor measurements must be recorded in millimeters (or decimal fractions of centimeters). For a lymph node to be considered pathologically enlarged and measurable, it must be ≥ 15 mm in short axis when assessed by CT scan (CT scan slice thickness recommended to be no greater than 5 mm).

Tumor lesions situated in a previously irradiated area, or in an area subjected to other loco-regional therapy, are not considered measurable unless there has been demonstrated progression in the lesion before study entry.

Non-measurable lesions are all other lesions, including small lesions (longest diameter <10 mm or pathological lymph nodes with ≥ 10 to <15 mm short axis), are considered non-measurable disease. Bone lesions, leptomeningeal disease, ascites, pleural/pericardial effusions, lymphangitis cutis/pulmonitis, inflammatory breast disease, and abdominal masses (not followed by CT or MRI), are considered as non-measurable.

5.6.2. Definitions of Response

Target Lesions: All measurable lesions up to a maximum of 2 lesions per organ and 5 lesions in total, representative of all involved organs, should be identified as **target lesions** and recorded and measured at baseline. Target lesions should be selected on the basis of their size (lesions with the longest diameter), be representative of all involved organs, and in addition should be those that lend themselves to reproducible repeated measurements.

A sum of the diameters (longest for non-nodal lesions, short axis for nodal lesions) for all target lesions will be calculated and reported as the baseline sum of diameters. If lymph nodes are to be included in the sum, then only the short axis is added into the sum.

Table 10. Target Lesion Evaluation

Response	Definition
Complete Response (CR)	Disappearance of all target lesions. Any pathological lymph nodes (whether target or non-target) must have reduction in short axis <10 mm
Partial Response (PR)	At least a 30% decrease in the sum of diameters of target lesions, taking as reference the baseline sum diameters
Progressive Disease (PD)	At least a 20% increase in the sum of diameters of target lesions, taking as reference the smallest sum on study (this includes the baseline sum if that is the smallest on study). In addition to the relative increase of 20%, the sum must also demonstrate an absolute increase of at least 5 mm. The appearance of one or more new lesions is also considered progression.
Stable Disease (SD)	Neither sufficient shrinkage to qualify for PR nor sufficient increase to qualify for PD, taking as reference the smallest sum diameters while on study.

Non-Target Lesions: All other lesions (or sites of disease) including any measurable lesions over and above the 5 target lesions should be identified as **non-target lesions** and should also be recorded at baseline. Measurements of these lesions are not required, but the presence or absence of each should be noted throughout the study.

Table 11. Non-Target Lesion Evaluation

Response	Definition
Complete Response (CR)	Disappearance of all extranodal non-target lesions. All lymph nodes must be non-pathological in size (<10 mm short axis).
Non CR/Non PD	Persistence of one or more non-target lesion(s)

Progressive Disease (PD)	Unequivocal progression of existing non-target lesions. The appearance of one or more new lesions is also considered progression
--------------------------	--

Symptomatic Deterioration: Subjects with a global deterioration of health status requiring discontinuation of treatment in Treatment Period 2 without objective evidence of disease progression at that time should be classified as having symptomatic deterioration. Reasonable efforts should be taken to obtain radiographic evidence to confirm disease progression. Subjects experiencing symptomatic deterioration during Treatment Period 1 are ineligible to enter Treatment Period 2 (as they do not meet the inclusion criteria requiring radiographic evidence of progression).

The baseline sum of diameters (from the Screening Visit) will be used as reference to further characterize disease control in the measurable dimension of the disease to determine the eligibility to continue participation in Treatment Period 2 of the study. From that point onward, the scan that led to those subjects' termination of Treatment Period 1 and eligibility to enter Treatment Period 2 will serve as a subject's new "baseline" measurements, with that sum of diameters used as reference to characterize the objective tumor response. CR and PR are defined as Objective Responses and must be confirmed by repeat assessment performed at least four weeks after the criteria for response are first met.

Table 12. Evaluation of Time Point Response: Patients with target (+/- non-target) disease*

Target Lesions	Non Target Lesions	New Lesions	Overall Response	Confirmation Scan (Treatment Period 2 only)
CR	CR	No	CR	Yes
CR	Non CR/Non PD	No	PR	Yes
CR	Not Evaluated	No	PR	Yes
PR	Non CR/Non PD/Not Evaluated	No	PR	Yes
SD	Non CR/Non PD	No	SD	No
PD	Any	Yes or No	PD	No
Any	PD	Yes or No	PD	No
Any	Any	Yes	PD	No

*Derived from *New Response Evaluation Criteria in Solid Tumours: Revised RECIST guideline (version 1.1)*, **Table 1, 2 & 3**

5.6.3. Evaluations of a Subject's Best Overall Response

The best overall response is the best response recorded from the start of Treatment Period 2 until disease progression/recurrence (taking as reference for progressive disease the smallest measurements recorded since the treatment started). The subject's best response assignment will depend on the achievement of both measurement and confirmation criteria.

Table 13. Best overall response when confirmation of CR and PR required*

Overall Response First Time Point	Overall Response Subsequent Time Point	Best Overall Response
CR	CR	CR
CR	PR	SD, PD or PR
CR	SD	SD provided minimum criteria for SD duration met, otherwise, PD
CR	PD	SD provided minimum criteria for SD duration met, otherwise, PD
CR	NE	SD provided minimum criteria for SD duration met, otherwise, NE
PR	CR	PR
PR	PR	PR
PR	SD	SD
PR	PD	SD provided minimum criteria for SD duration met, otherwise, PD
PR	NE	SD provided minimum criteria for SD duration met, otherwise, NE

*Derived from *New Response Evaluation Criteria in Solid Tumours: Revised RECIST guideline (version 1.1)*, Table 5

First Documentation of Response: The time between the initiation of Treatment Period 2 and the first documentation of PR or CR.

Confirmation of Response: To be assigned a status of CR or PR, tumor measurements must be confirmed by repeat assessment performed at least four weeks after the criteria for response are first met.

Duration of Response: The period of time from the disease assessment at which measurement criteria are first met for CR or PR (whichever status is recorded first) until the first date that recurrent or progressive disease is objectively documented.

Duration of Complete Response (CR): The period of time from the disease assessment at which criteria for CR are met until the first date that recurrent disease is objectively documented.

Duration of Stable Disease: The time from the initiation of combination therapy on Study Visit 1 in Treatment Period 2 until the criteria for disease progression are first met.

Disease Control: Disease control is defined as all Best Overall Responses that are not progressive disease (i.e. SD, PR or CR).

5.7. Safety Assessments

5.7.1. Concomitant Medication

Concomitant medication is defined as any medication, other than the investigational medicinal product (Sodium Cridanomod) and megestrol acetate, taken at any point in the duration from the Screening Visit until the End of Study Visit or the Safety Follow-up Visit. This includes all prescription medications, over-the-counter medications, and herbal remedies. All concomitant medications will be recorded.

5.7.2. Vital Signs

The subject will undergo an assessment of vital signs (systolic and diastolic blood pressure, heart rate and body temperature) after 5 minutes in a supine position at the Screening Visit, at all Study Visits, at the End of Study Visit, and at the Safety Follow-up Visit.

5.7.3. Laboratory Assessments

Hematology, biochemistry, and urinalysis samples will be analyzed by the local laboratory using standard methods.

5.7.3.1. Hematology

Blood samples (5 mL) will be taken at the Screening Visit, at each Study Visit, at the End of Study Visit, and at the Safety Follow-up Visit and used for routine hematology analysis.

Hematology profile will include:

- Hemoglobin value
- Hematocrit
- Mean corpuscular volume (MCV)
- Mean corpuscular hemoglobin concentration (MCHC)
- Erythrocytes
- Leucocytes
- Differential leukocyte count (neutrophils, lymphocytes, monocytes, eosinophils and basophils)
- Platelet count

5.7.3.2. Serum Chemistry

Blood samples (5 mL) will be taken at the Screening Visit, at each Study Visit, at the End of Study Visit, and at the Safety Follow-up Visit and used for routine serum chemistry analysis.

Chemistry profile will include:

- Phosphate
- Sodium
- Potassium
- Chloride
- Calcium
- Bicarbonate
- Creatinine
- Creatine kinase
- Glucose
- Blood urea nitrogen (BUN)
- Total proteins
- Albumin

- Total bilirubin
- Alkaline phosphatase
- Lactate dehydrogenase (LDH)
- Serum glutamic oxaloacetic transaminase (SGOT) / Aspartate aminotransferase (AST)
- Serum glutamic pyruvic transaminase (SGPT) / Alanine aminotransferase (ALT)

Estimated Glomerular Filtration Rate (eGFR) will be calculated based on blood creatinine levels and subject demographics using the CKD Epidemiology Collaboration (CKD-EPI method¹⁴.

5.7.3.3. Urinalysis

Urine samples are taken at the Screening Visit, at the End of Study Visit, at Visit 7, at Visit 13 and every 12 weeks thereafter until disease progression, and at the Safety Follow-up Visit.

Urine analysis will include:

- Blood
- Protein
- Glucose
- Ketones
- pH

5.7.4. Pregnancy Test

Pregnancy tests are applicable to all subjects of childbearing potential (i.e. excluding those who are anatomically sterile or are post-menopausal). A serum pregnancy test (measuring β -human chorionic gonadotropin [β -hCG]) will be performed at the Screening Visit, and a urine pregnancy test will be performed at Visit 7 at the End of Study Visit, and at the Safety Follow-up Visit.

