Estimated Time Schedule	
First subject enrolled: September 2017 Recruitment completed: September 2018 Last subject completed the study: January 2021

STUDY DESIGN AND ASSESSMENT SCHEDULE

Figure 1: Study Flow Chart

[figure not shown]

Table 1: Screening Schedule of Assessments

Screening	
Study Calendar (Weeks)	-18 to -15
Procedures and Assessments	
Informed consent	X
Eligibility Criteria	X
Demographics	X
Medical History	X
Concomitant Medication	X
Physical Exam	X
Vital Signs	X
Height	X
Weight	X
Performance Status	X
CBC w/ diff, platelets	X
Serum chemistry ^A	X
eGFR	X
Urinalysis	X
Serum Pregnancy Test (B-hCG) ^B	X
ECG	X
Assessment of Adverse Events	X
PrR status of archived tumor tissue determined by central lab	X
Imaging (CT/MRI) ^E	X
Tumor Assessment (using RECIST criteria) ^E	X
Footnotes	
A - Phosphate, sodium, potassium, chloride, calcium, bicarbonate, creatinine, creatine kinase, glucose, blood urea nitrogen (BUN), total proteins, albumin, total bilirubin, alkaline phosphatase, LDH, SGOT/AST, SGPT/ALT.	
B - For women of childbearing potential.	
E - Screening tumor assessments must be performed <10 days before Visit -3.	

Table 2: TP1 Schedule of Visits and Assessments

	Treatment Period 1 (PrR Positive Patients Only)				Subjects Ineligible to enter TP2 or who Withdraw Early
	-3	-2	-1	TP1-EXT	
Study Visits	-3	-2	-1	TP1-EXT	End of Study (EOS)
Study Calendar (Weeks)	-14	-8	-2	+12 wks	+ 2 weeks
Treatments					
Progestin therapy (Megestrol acetate) Dispensing/Return ^F	D	R/D	R/D	R/D	R
Procedures and Assessments					
Eligibility Criteria	X				
Concomitant Medication	X	X	X	X	X
Physical Exam	X ^C	X	X	X	X
Vital Signs	X	X	X	X	X
Weight	X ^C	X	X	X	X
Performance Status	X ^C	X	X	X	X
CBC w/ diff, platelets	X ^C	X	X	X	X
Serum chemistry ^A	X ^C	X	X	X	X
eGFR	X ^C	X	X	X	X
Urinalysis					X
Urine Pregnancy Test ^B					X
ECG	X ^H	X ^H	X ^H	X ^H	X
Blood Draw (for PK sub-study) ^G	X ^G				
Assessment of Adverse Events	X	X	X	X	X
Imaging (CT/MRI)			X	X ^D	
Tumor Assessment (using RECIST criteria)			X	X ^D	
Patient Diary Issue/Collection ^F	I	I/C	I/C	I/C	C
Subject Compliance		X	X	X	X
Footnotes					
A - Phosphate, sodium, potassium, chloride, calcium, bicarbonate, creatinine, creatine kinase, glucose, blood urea nitrogen (BUN), total proteins, albumin, total bilirubin, alkaline phosphatase, LDH, SGOT/AST, SGPT/ALT.					
B - For women of childbearing potential.					

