3.5. Exclusion Criteria

1. Mixed histology of the tumor or evidence of tumor histology other than serous carcinoma or endometrioid type of endometrial carcinoma;
2. Concurrent systemic corticosteroid therapy;
3. Concurrent oral contraceptive use / Women of childbearing potential not using highly effective means of contraception;
4. Pregnancy confirmed by pregnancy test / Lactating women (for women of childbearing potential);
5. Prior therapy with hormonal progestin agents;
6. Patients who are candidates for treatment with standard chemotherapy agents (there is no limit to the number of lines of prior chemotherapy);
7. History of blood clot;
8. History of known bleeding disorder (i.e. disseminated intravascular coagulation or clotting factor deficiency);
9. Major surgery within 4 weeks prior to the start of the study;
10. Patients with clinically significant illnesses which, according to the Investigator, could compromise participation in the study;
11. History of other clinically active malignancies within 5 years, except for carcinoma in situ of the cervix, basal cell carcinoma, or squamous carcinoma of the skin.
12. Known hypersensitivity or idiosyncratic reaction to any of the study drugs (Sodium Cridanimod, megestrol acetate, lidocaine) and excipients;
13. Patients with known brain metastases;
14. Patients currently receiving any other investigational agents;
15. Patients currently receiving any other anticancer therapies;
16. Participation in any other clinical study within the last 4 weeks prior to the start of the study;

Waivers to the exclusion criteria will **NOT** be allowed.

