5.4. Visit Schedule and Required Study Procedures

5.4.1. Screening (Time Frame: ≤ 4 weeks from the start of Treatment Period 1, Week -18 to -15)

- Informed consent
- Eligibility criteria
- Demographics
- Medical history
- Concomitant medication review
- Physical exam
- Vital signs

- Height
- Weight
- Performance status
- CBC with differential, platelets
- Serum chemistry
- eGFR
- Urinalysis
- Serum pregnancy test (for women of childbearing potential)
- ECG
- AE evaluation
- Confirmation of PrR status in central laboratory of archived tumor sample (*Specimen should be sent to central lab during Screening Weeks -18 and -16 to ensure results are received prior to Study Visit -3*).
- CT/MRI Scan
- Tumor assessment and measurements (*Radiologic evaluation must be obtained within 10 days of Visit -3*).

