- Concomitant medication review
- Physical exam
- Vital signs
- Weight
- Performance status
- CBC with differential, platelets
- Serum chemistry
- eGFR
- Urinalysis
- Urine Pregnancy Test (for women of childbearing potential)
- ECG
- AE evaluation
- Collect any outstanding patient diaries
- Collect all remaining megestrol acetate supplies

Subjects determined to have PrR negative status and subjects with documented disease progression after completing Treatment Period 1, will be eligible to enter Treatment Period 2.

Treatment Period 2

Visit 1, Day 0 (+/- 3 days) (Combination Treatment Start)

- Eligibility criteria
- Concomitant medication review
- Physical exam
- Vital signs
- Weight
- Performance status
- CBC with differential, platelets
- Serum chemistry
- eGFR
- ECG (before administration of Sodium Cridanimod and megestrol acetate, and 15, 60, 120, and 360 (\pm 5) minutes after administration of Sodium Cridanimod)
- For optional PK Sub-Study Participants:
 - Collection of blood samples for optional PK sub-study, at 10 timepoints: 0 min (before administration of Sodium Cridanimod and megestrol acetate), and 15 min, 30 min, 45 min, 60 min, 90 min, 2 hr, 3 hr, 4 hr, and 6 hr (all times +/- 2 minutes) after administration. Note additional PK draws below**
- AE evaluation
- Assess subject dosing compliance
- Collect completed patient diaries and remaining megestrol acetate for subjects completing Treatment Period 1
- Issue patient diaries
- Dispense supply of megestrol acetate
- Administration of megestrol acetate
- First administration of Sodium Cridanimod – The subject's condition will be monitored closely for a one-hour period after this first administration.

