11.5 Pregnancy Testing

Pregnancy tests are applicable to all subjects of childbearing potential (i.e. excluding those who are anatomically sterile or are post-menopausal). A serum pregnancy test (measuring *-human chorionic gonadotropin [β -hCG]) will be performed at the Screening Visit, and a urine pregnancy test will be performed at the End of Study-TP1 Visit, at Visit 7, Visit 13, and the Safety Follow-Up TP2 Visit. Results of pregnancy testing will be reported in a subject listing.

12 Concomitant Medications

Concomitant medication is defined as any medication, other than the investigational medicinal product (SC) and MA, taken at any point in the duration from the Screening Visit until the End of Study-TP1 Visit

or the Safety Follow-Up TP2 Visit. This includes all prescription medications, over-the-counter medications, and herbal remedies. All concomitant medications will be recorded. A subject listing of concomitant medications will be provided. Medications administered prior to first dose of study drugs will be distinguished from those administered once study drug dosing has begun.

13. Dosing Compliance and Treatment Exposure

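### No repeat pregnancy test is scheduled between Screening and the first Sodium Cridanimod dose for women of childbearing potential who move from Period 1 to Period 2

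*Protocol*

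**What the plan says.** Protocol 5.7.4 requires a serum test at Screening for women of childbearing potential and then states that "a urine pregnancy test will be performed at Visit 7 at the End of Study Visit, and at the Safety Follow-up Visit". Section 5.4.1 dates Screening as "Time Frame: ≤ 4 weeks from the start of Treatment Period 1, Week -18 to -15".

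In Table 2 (Period 1) the urine test is marked in one column only, the End of Study Visit, which is headed "Subjects Ineligible to enter TP2 or who Withdraw Early". The visit list in section 5.4.2 describes the same group: women who stop during Period 1 and women whose disease is still controlled at TP1-EXT. In Table 3 (Period 2) the test is marked at Visit 7 (Week 24) and at Safety Follow-up. Visit 1 is where the first Sodium Cridanimod dose is given. It carries an eligibility item but no pregnancy test, in both Table 3 and the section 5.4.2 list.

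Exclusion 4 in section 3.5 reads "Pregnancy confirmed by pregnancy test / Lactating women (for women of childbearing potential". Exclusion 3 bars women of childbearing potential who lack effective contraception, and section 3.7 requires contraception from screening to completion or withdrawal. Section 5.9.7 requires withdrawal if pregnancy occurs at any time.

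SAP 11.5 gives a longer list: "a urine pregnancy test will be performed at the End of Study-TP1 Visit, at Visit 7, Visit 13, and the Safety Follow-Up TP2 Visit".

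**The concern.** Period 1 can last up to 24 weeks, and the test schedule has no step at the point where a woman crosses from megestrol alone to the investigational drug. The one urine test in Period 1 falls on women leaving the trial. Women about to start Sodium Cridanimod rely on the Screening result.

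Other safety assessments are treated differently. Blood count, chemistry, eGFR, physical examination, weight and performance status are repeated at Visit -3 if more than 7 days have passed since Screening, and all are done again at Visit 1. Pregnancy is an exclusion defined by a test, yet its result is not refreshed, and the documents give no reason.

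At stake is the start of combination treatment on an out-of-date result, in a trial whose own rule is that pregnancy ends participation. The route concerned is planned to supply 30–32 of the Period 2 subjects (Protocol 7.1), although only a few of them would be of childbearing potential.

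**Working it through.** **Step 1: which visits carry a test for a woman who goes from Period 1 to Period 2**

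| Visit | Nominal week | Pregnancy test? | Source |
|---|---|---|---|
| Screening | -18 to -15 | Serum | Table 1, 5.4.1, 5.7.4 |
| Visits -3, -2, -1 | -14, -8, -2 | None | Table 2, 5.4.2 |
| TP1-EXT (if used) | 12 weeks after Visit -1 | None | Table 2, 5.4.2 |
| End of Study Visit | – | Urine, but she does not attend | Table 2, 5.4.2 |
| Visit 1 | Start of Period 2 | None | Table 3, 5.4.2 |
| Visit 7 | Week 24 of Period 2 | Urine | Table 3, 5.4.2, 5.7.4 |

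The tables, the visit lists and section 5.7.4 all agree on this, so it is not a misprint in one place.

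**Step 2: age of the Screening result at Visit 1**

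I used the nominal study calendar and ignored visit windows. Age = week of Visit 1 minus week of Screening (-15 or -18).

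- *Earliest permitted entry* (progression after 4 weeks of megestrol): Visit 1 at -14 + 4 = week -10. Age = -10 + 15 = 5 to -10 + 18 = 8 weeks.
- *Progression at the 12-week scan:* Visit 1 at week 0. Age = 15 to 18 weeks. Table 2 footnote D lets Visit 1 follow once measurements are available. If that were at once, Visit 1 would be at week -2 and the age 13 to 16 weeks.
- *Progression at the 24-week scan:* TP1-EXT at -2 + 12 = week 10, and Visit 1 up to 2 weeks later at week 12. Age = 12 + 15 = 27 to 12 + 18 = 30 weeks. If Visit 1 follows the scan at once, the age is 10 + 15 = 25 to 10 + 18 = 28 weeks. The range is therefore 25–30 weeks.

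**Step 3: interval from the Screening test to the next scheduled test**

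Add 24 weeks, since Visit 7 is at Week 24 of Period 2.

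- Earliest entry: 29–32 weeks.
- After the 12-week scan, Visit 1 at week 0: 39–42 weeks.
- After the extension, Visit 1 at week 12: 51–54 weeks.

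The overall span is 29–54 weeks.

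**Step 4: how many women**

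Protocol 1.1.1 says more than 90% of diagnosed women are older than 50. If that held in this trial, fewer than 10% of the 30–32 planned entrants from Period 1 would be 50 or younger: 0.10 × 30 = 3.0 to 0.10 × 32 = 3.2, so about 3 at most. Section 5.7.4 also exempts women who are anatomically sterile or post-menopausal. Age 50 is only a rough stand-in for childbearing potential.

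**Step 5: Visit 13**

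SAP 11.5 names a urine test at Visit 13. Protocol 5.7.4, Protocol Table 3 and the Visit 13 list in Protocol 5.4.2 do not. The SAP's own Period 2 schedule (4.6.3) does not either, so the SAP disagrees with itself as well as with the protocol.

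**The case against.** The case for leaving the schedule alone has real substance.

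- **There is a test before the first dose.** A reader looking only at the Visit 1 column might infer that these women start Sodium Cridanimod untested. That is wrong: a serum test at Screening precedes all study drug. What is missing is a repeat.
- **The eligibility item at Visit 1 may not cover exclusion 4.** A reader might infer that the protocol re-applies every exclusion at Visit 1 and so sets itself a check it cannot perform. The documents do not say this. Exclusion 5 bars prior progestin therapy, so re-applying the full list would exclude every entrant from Period 1. The only criterion labelled for Period 2 is inclusion 15. The item does not state its scope, so there is something to clarify, but the gap in testing does not depend on how it is read.
- **Other safeguards exist.** Contraception is required throughout, Period 2 visits are every 4 weeks up to Week 48, and abdominal and pelvic imaging is done before entry and at Week 12. It would go too far to say that a pregnancy would remain unrecognised for 24 weeks; only scheduled pregnancy testing is absent for that time. These measures lower the risk but are not a pregnancy test, and the protocol schedules later tests despite them.
- **The difference from PrR-negative entrants is partly assumed.** If Visit 1 takes the place of Visit -3 for them, their Screening result is about 1–4 weeks old (-14 + 15 = 1 to -14 + 18 = 4). Section 5.4.1 dates Screening only against the start of Period 1, which they skip, so the documents do not guarantee that interval.
- **The trial is closing early.** The SAP reports 25 women enrolled and an abbreviated analysis. A change to the visit schedule may now have little practical reach. Pregnancy results are still to be listed (Listing 16.2.4.6), so the SAP wording on Visit 13 remains relevant.

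**Conclusion.** The gap is real and limited. Following the plan as written, a woman of childbearing potential who progresses in Period 1 begins the investigational drug on a Screening result that is 5–8, 15–18 or about 25–30 weeks old, depending on her route of entry. She is next tested 29–54 weeks after Screening. These figures rest on the nominal calendar without visit windows, on entry after 4 weeks of megestrol as the earliest case, and on TP1-EXT falling 12 weeks after Visit -1.

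The number affected is small: about 3 at most of the planned 30–32, if the protocol's general age figure applies. This is a safety improvement worth making, not a flaw that affects any efficacy result. The Visit 13 mismatch is clerical and separate.

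**What to change.** Reconcile exclusion 4 and the Visit 1 eligibility item with the test schedule in Table 3, section 5.4.2 and section 5.7.4, so that pregnancy status is current when Period 2 treatment starts. State which criteria the Visit 1 item covers. One way is to use, at the existing Visit 1, the urine test already scheduled elsewhere. The timing is for the sponsor and the clinical team to settle.

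Separately, make SAP 11.5, SAP 4.6.3, Protocol 5.7.4, Protocol Table 3 and the Visit 13 list agree on whether Visit 13 includes a pregnancy test.

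The cost is one urine test for each of the few women concerned, at a visit they already attend, plus wording changes in both documents. No extra visit is needed and no analysis changes.
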